11.4 Supplementary Analysis Plans

11.4.1 Secondary Endpoints

11.4.1.1 The efficacy of early integrated palliative care (PC) on patient reported outcomes in patients with newly diagnosed incurable lung or non-colorectal gastrointestinal cancer will be assessed by analyzing:

1. Change in QOL on the FACT over time
2. Rate of depressive symptoms as per HADS at 12 weeks and over time
3. Rate of anxiety symptoms as per HADS at 12 weeks and over time
4. Change in illness understanding over time

11.4.1.2 The efficacy of early integrated palliative care (PC) on family caregiver reported outcomes in those with newly diagnosed incurable lung or non-colorectal gastrointestinal cancer will be assessed by analyzing:

1. Change in QOL on the SF-36 over time
2. Rate of depressive symptoms as per HADS at 12 weeks and over time
3. Rate of anxiety symptoms as per HADS at 12 weeks and over time
4. Change in illness understanding over time

11.4.1.3 The impact of early, integrated PC on quality of EOL care and resource utilization in patients with newly diagnosed incurable lung or non-colorectal gastrointestinal cancer will be assessed by analyzing:

1. Rate of referral, enrollment and length of stay on hospice
2. Location of death
3. Number of hospital and ICU admissions and days
4. Chemotherapy and radiation administration
5. Overall survival

11.4.1.4 Concordance between patient and family caregiver report of prognosis/curability.

11.4.2 Secondary Analysis

We will adopt the gatekeeping procedure for the primary analysis of efficacy of early PC on patient reported outcomes, the secondary analysis of efficacy of early PC on family caregiver reported outcomes, and the secondary analysis of impact of early PC on quality of EOL care and resource utilization. Therefore, they will be tested at the 5% significance level in sequence, and the subsequent analysis (hypothesis testing) will only be carried out if the previous analysis is statistically significant. Otherwise, subsequent analysis will be descriptive in nature. Multiplicity will not be adjusted for other secondary analyses, hence, statistically significant findings from secondary analyses are exploratory in nature and therefore shall be interpreted as such. Descriptive statistics and graphical approaches will form the basis for most secondary analyses.

- 11.4.2.1** To assess the changes in QOL over time among patients, generalized linear model with repeated measures will be used for comparison between treatment arms. To compare rates of psychological distress between treatment arms, we will transform the HADS score into a dichotomous outcome with categories reflecting the presence or absence of clinically significant depression and anxiety. We will then use generalized linear models with repeated measures to assess the association between the presence of depression/anxiety and study arm, using risk difference and relative risk to compare proportions between the study arms. To compare the illness understanding, we will analyze each item of the PTPQ separately using the appropriate test to determine the significance of the between-group differences. To assess additional measures of family caregiver perceptions of quality of death, we will employ the Jonckheere-Terpstra test, which is appropriate for contingency tables with ordinal data.
- 11.4.2.2** To assess the changes in QOL among family caregivers, we will use the similar approach as for QOL among patients. Change in the total score and subscales will be compared with generalized linear models with repeated measures. Analysis of psychological distress and illness understanding will be the same as above.
- 11.4.2.3** To assess differences in quality of EOL care, we will use Fisher's exact test to determine the association between the composite EOL care measure categories and study arm and a comparison of rates between the groups based on the risk difference and relative risk. To assess the difference in resource utilization, we will also compare days on hospice and in the hospital and ICU using the Mann-Whitney U test. To compare patient survival, we will use Kaplan-Meier estimates, testing the difference between the curves with the log-rank test.
- 11.4.2.4** To assess the concordance between patient and family caregiver report of prognosis/curability, we will analyze each of the primary and secondary endpoints using the matched-pair subset. Simple tests such as paired *t*-test, Wilcoxon signed-rank test, and generalized linear models for matched pair data will be utilized.

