1.3 Hypotheses

Aim 1: To determine the efficacy of early, integrated palliative care (PC) on patient and family caregiver reported outcomes in those with newly diagnosed incurable lung or non-colorectal gastrointestinal cancer.

- Hypotheses 1: Compared to patients receiving standard care (SC), patients receiving early PC will (1) experience improved QOL and fewer depressive symptoms; and (2) report a more accurate understanding of their terminal illness and the goals of care.
- Hypotheses 2: Compared to family caregivers in the SC arm, family caregivers of patients receiving early PC will (1) experience improved QOL and fewer depressive symptoms throughout the course of the patient's illness; and (2) report a more accurate understanding of the patient's terminal illness and the goals of care.

Aim 2: To assess the impact of early, integrated PC on quality of EOL care and resource utilization in patients with newly diagnosed incurable lung or non-colorectal gastrointestinal cancer

- Hypotheses: Compared to patients receiving SC, patients receiving early PC will (1) receive higher quality EOL care (i.e., less chemotherapy in the last 14 days of life, greater utilization of hospice services, and/or length of stay in hospice > 3 days); (2) experience less hospital and ICU days and (3) have at least the same survival as patients receiving standard care

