9.0 MEASURES

Demographics: All study participants will complete a demographic questionnaire (see Appendix III for patient, Appendix IV for family caregiver) at the time of baseline data collection detailing their age, sex, race, ethnicity, religion, relationship status, education level, annual household income, and living situation (specify number of dependent children living at home). Family caregivers will also specify their relationship with the patient, living situation (specify number of dependent children living at home) and employment status.

QOL-Patient: To assess quality of life over time in study patients, we will use the Functional Assessment of Cancer Therapy (FACT) Questionnaires, which have been validated for use in multiple care settings and with diverse tumor types. The FACT consists of four subscales assessing well-being across four domains (physical, functional, emotional and social) during the prior seven days. Additional questions specific to cancer symptoms will be added to the measure for each tumor type, including lung (FACT-L), esophageal and gastric (FACT-E), and hepatic, biliary, and pancreatic (FACT-Hep) – See Appendix III.⁵⁸⁻⁶¹ Patients will complete this questionnaire at baseline, 6, 12 and 24 weeks.

QOL-Family caregiver: We will use short-form health survey (SF-36) to assess change in health-related QOL over time in family caregivers (see Appendix IV).⁶² The SF-36 measures eight domains of health-related quality-of-life: physical functioning, role limitations due to physical health, bodily pain, general health perceptions, vitality, social functioning, role limitations due to emotional health, and mental health. Family caregivers will complete this questionnaire at baseline, 6, 12 and 24 weeks.

Mood: We will use the Hospital Anxiety and Depression Scale (HADS) to assess symptoms of depression and anxiety in all study participants (see Appendix III for patient, Appendix IV for family caregiver).⁶³ The HADS is a 14-item questionnaire that contains two 7-item subscales assessing depression and anxiety symptoms during the past week. Scores on each subscale range from 0 to 21, with a cutoff of 8 or greater denoting clinically significant depression or anxiety symptoms. Patients and family caregivers will complete questionnaire at baseline, 6, 12 and 24 weeks.

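### HADS is compared between arms only as below 8 versus 8 or more; adding the continuous score beside the rate would recover power for the mood hypothesis at little cost

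*Combined protocol and SAP*

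**What the plan says.** Section 1.3 hypothesises that "patients receiving early PC will (1) experience improved QOL and fewer depressive symptoms"; a parallel hypothesis covers family caregivers. Neither mentions anxiety.

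Section 9.0 describes the instrument: "Scores on each subscale range from 0 to 21", "with a cutoff of 8 or greater denoting clinically significant depression or anxiety symptoms". Patients and caregivers complete it at baseline and at weeks 6, 12 and 24.

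Section 11.4.1.1 lists the patient endpoint as "Rate of depressive symptoms as per HADS at 12 weeks and over time", with a matching line for anxiety. Section 11.4.1.2 repeats both for caregivers.

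Section 11.4.2.1 gives the analysis: "we will transform the HADS score into a dichotomous outcome with categories reflecting the presence or absence of clinically significant depression and anxiety". The dichotomised outcome then enters a generalized linear model with repeated measures, "using risk difference and relative risk to compare proportions between the study arms". For caregivers, 11.4.2.2 says: "Analysis of psychological distress and illness understanding will be the same as above".

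FACT and SF-36 are compared between arms as scores. The paired tests in 11.4.2.4 concern patient-caregiver concordance, so they do not supply a between-arm comparison of the HADS score.

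**The concern.** A hypothesis about fewer symptoms can be true without many people crossing a threshold. Under the plan, a patient who falls from 14 to 9 counts as unchanged, and one who falls from 8 to 7 counts as a success. If the intervention lowers symptoms across the whole range, cutting at 8 throws away part of that signal.

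The sample size in 11.2.1 was set for FACT, and no power is given for HADS, so the mood endpoints have whatever power the trial happens to leave them. The caregiver sample is smaller still. The practical risk is that an inconclusive comparison of rates is read as evidence of no mood benefit when the score, already collected, might have shown one.

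**Working it through.** **Inputs from the documents.** Section 11.2.1: 140 per arm, 80% power, 4 points, SD 11.87, two-sided 5%; 20-30% missing; 200 enrolled per arm; about 300 caregivers. Section 9.0: subscale range 0-21, cutoff 8.

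**Assumptions.** The documents give no HADS SD, effect or rate. These are varied below.

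**1. The plan's own figure.** For a difference of means, power ≈ Φ(d·√(n/2) − 1.96).
- d = 4/11.87 = 0.337. With n = 140, 0.337 × 8.367 − 1.96 = 0.86, so power = 80.5% (80.2% with the noncentral t). The n needed is 139. The stated 140 and 80% reproduce.
- With 30% missing, 200 × 0.70 = 140; with 20%, 200 × 0.80 = 160.
- Caregivers: 300/2 = 150 per arm. If 30% are missing, as assumed for patients, 150 × 0.70 = 105.

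**2. What a cut costs in a simple model.** Let the score be normal, with a proportion p of controls at or above the cut, and let the whole distribution shift by d. The treated proportion is 1 − Φ(c + d), where c = Φ⁻¹(1 − p). The share of information kept is φ(c)²/[p(1 − p)].
- Example, p = 25%, d = 0.337: c = 0.674 and the treated rate is 15.6%. Two-proportion power = Φ{[0.094·√140 − 1.96·√(2 × 0.203 × 0.797)]/√(0.1875 + 0.1317)} ≈ 50%, against 80.5% for the score. Information kept: 0.318²/0.1875 ≈ 54%.
- For p from 15% to 50%, power for the cut runs from 39.5% to 61%, and 43% to 64% of the information is kept.

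**3. Scores on the HADS scale.** Simulated gamma-shaped scores, rounded and clipped to 0-21, SD 4 in controls, 1.2-point difference, control means 5, 6 and 7. A t-test of the score is compared with a two-proportion test at 8 or more. Ranges span the three means; simulation error is a point or two.

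| Per arm | SD model | Score | Cut at 8 |
|---|---|---|---|
| 140 (patients) | equal in both arms | 73-74% | 30-51% |
| 140 (patients) | falls in proportion to the mean | 79-81% | 60-62% |
| 105 (caregivers) | equal in both arms | 59-60% | 24-38% |
| 105 (caregivers) | falls in proportion to the mean | 64-69% | 46-49% |

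A closed-form check on the equal-SD score column: d = 1.2/4 = 0.30 gives Φ(0.30 × 8.367 − 1.96) = 71% at 140 and Φ(0.30 × 7.246 − 1.96) = 58% at 105. These sit just below the simulated values, as expected because clipping trims the SD slightly.

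**4. Other effect shapes.** Skewed integer scores from a negative binomial capped at 21 gave 70-79% for the score against 49-53% for the cut, a loss of 18-27 points. If the entire effect is confined to patients at 8 or more, the ranking reverses: about 98-99.5% for the cut against 80-91% for the score. That is an extreme case, but it shows that the direction is not guaranteed.

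**The case against.** The strongest reply is that the plan is consistent with itself. The objectives in 2.2.1 and 2.2.2 point to the endpoints in 11.4.1, those endpoints are rates, and the analysis compares rates with measures suited to rates. The cutoff is fixed in advance and clinically defined, so there is no data-driven cutpoint, no bias and no inflation of the error rate. A patient at 9 still has what section 9.0 counts as clinically significant symptoms. All of this stands.

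A reader might therefore go too far in three ways. One is to infer that the dichotomised analysis is wrong, or that it contradicts its endpoint. It does neither; the looser fit is only with the hypothesis in 1.3, whose wording does not itself demand a mean score. Another is to extend the hypothesis mismatch to anxiety, for which 1.3 states no hypothesis. The third is to conclude that the mean score should replace the rate as the tested comparison. That would demote a declared endpoint, leave 11.4.1 out of step with 11.4.2 unless it too were rewritten, and give up the more clinical measure.

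It is also fair that no HADS power is claimed, that 11.4.2 labels unadjusted secondary findings exploratory, and that the primary endpoint is untouched. The simulation tests a single time point. Repeated measures add information to both analyses, so they do not by themselves remove the loss.

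**Conclusion.** The point holds as a modest matter of efficiency. HADS is compared between arms only at the cut of 8, and over the models in which symptoms fall across the range the cost is about 18 to 44 percentage points of power at 140 per arm. The size rests on an assumed SD of 4, a 1.2-point difference, control means of 5 to 7 and the shape of the effect. No single pair of power figures should be quoted as the loss, and an effect concentrated in patients above the cutoff could make the rate the more powerful measure.

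For depression, the score would give the trial a better chance of answering its own hypothesis under most of these models. For anxiety, the argument is power alone. In caregivers, power is lower for either measure because fewer are expected. Caregiver outcomes also form a step in the gatekeeping sequence of 11.4.2, but the plan does not say which caregiver endpoint carries that step, so a reader should not infer that the cut on HADS would block later testing.

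**What to change.** Keep the rate at 8 or more, with risk difference and relative risk, as the declared endpoint. Then:

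- In 11.4.2.1 and 11.4.2.2, add a prespecified between-arm comparison of the continuous HADS-D and HADS-A scores at week 12, from the repeated-measures model adjusted for baseline.
- In 11.4.1.1 and 11.4.1.2, list that comparison, so that endpoints and analyses agree.
- State that the added comparisons sit outside the gatekeeping sequence and are exploratory, and settle the wording before any between-arm HADS results are seen.

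No form, visit or participant is added. The cost is a few sentences, a little analysis and one more comparison per subscale in each population, already covered by the statement in 11.4.2 that unadjusted secondary findings are exploratory. Because 11.6.2 commits the secondary endpoints to ClinicalTrials.gov, the additions would need reporting there too. A mean difference is less directly clinical than a rate, which is why the rate stays beside it.

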7.1.2 Subsequent Medical Oncology/Infusion Visits

- A PC clinician will meet with patients randomized to early PC within one month of registration. This should be done at the patient's next medical oncology or infusion visit following registration.
- The PC clinician will meet with patients and family caregivers (if present at the appointments) at a minimum of every four weeks in the outpatient care setting (oncology clinic or infusion suite). PC visits will be coordinated with regularly scheduled cancer center appointments to reduce burden of multiple hospital visits.
- If patients are unable to come to the clinic for a scheduled PC visit, at least one attempt will be made to reschedule the visit within seven days of the scheduled PC visit. If a rescheduled in-person visit is not feasible, the PC clinician will conduct the visit over the telephone and document the content and nature of the visit in the medical record. Clinic visits are strongly preferred to telephone visits and should be attempted as much as possible.
- Patients, family caregivers, or the PC team may initiate consultations as needed.
- PC clinicians should follow the guidelines as detailed in Appendix I.
- Depending on clinic space, workflow, and patient preference, PC clinicians may see patients in the clinic or in the chemotherapy infusion room.
- If a patient is admitted to the hospital during the study period, they should be seen at least once by either their outpatient palliative care clinician or the inpatient palliative care hospital based team. Additional follow up during the hospital admission is not dictated by the study requirements and patients should be followed as per their institution practice.

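### The HADS depression and anxiety analysis names no week-12 contrast and leaves the role of baseline HADS open; stating both would match the endpoint and gain power at almost no cost

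*Combined protocol and SAP*

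**What the plan says.** Section 11.4.1.1 lists, for patients, "Rate of depressive symptoms as per HADS at 12 weeks and over time", with a parallel entry for anxiety. Section 11.4.1.2 repeats both for family caregivers. Section 9.0 gives the schedule: "Patients and family caregivers will complete questionnaire at baseline, 6, 12 and 24 weeks". It also gives the threshold: "with a cutoff of 8 or greater denoting clinically significant depression or anxiety symptoms".

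Section 11.4.2.1 describes the analysis. First, "we will transform the HADS score into a dichotomous outcome with categories reflecting the presence or absence of clinically significant depression and anxiety". The test comes next: "We will then use generalized linear models with repeated measures to assess the association between the presence of depression/anxiety and study arm". The effect measures are a risk difference and a relative risk. Section 11.4.2.2 extends this to caregivers: "Analysis of psychological distress and illness understanding will be the same as above".

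None of these sentences names a visit for the risk difference, a visit or arm-by-visit term, or a role for the baseline HADS value. FACT is treated differently. Section 11.3.2 enters all the repeated FACT measures in one model, names the change from baseline to week 12 as the target, and counts baseline among the four time points.

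Baseline questionnaires are completed on the day of registration (7.1.1, 7.2.1). The intervention starts later: "A PC clinician will meet with patients randomized to early PC within one month of registration".

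**The concern.** The endpoint has two parts, and the analysis sentence separates neither. An analyst could fit a single arm term over all visits, an arm-by-visit model with a week-12 contrast, or a model with baseline as covariate. Each would satisfy the text, and each gives a different risk difference. Nothing prevents that choice from being made after the data are seen.

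One of these readings does damage. If baseline is a response row under one arm term, a quarter of the rows come from a visit where randomization makes the true difference zero, and the reported effect shrinks accordingly. Week 6 may add to this, because the first palliative care contact can fall only about two weeks earlier.

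Whichever model is meant, the plan also leaves unused a strong predictor that it already collects: the participant's own baseline HADS score.

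Mood is named in Hypotheses 1 and 2 (section 1.3), and the caregiver outcomes form a step in the 5% testing sequence of 11.4.2. That justifies a precise definition even for secondary endpoints.

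**Working it through.** **Inputs from the documents.** Four HADS occasions, one of them before the intervention (6.2, 6.3, 9.0). 1:1 allocation (1.4). 140 analysable patients per arm (11.2.1).

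**The plan's own figure.** Section 11.2.1 covers FACT only: 2 × (1.96 + 0.842)² × 11.87² / 4² = 138.2, so 139 per arm. The t-test solution is 139.2, so 140. Allowing 30% missing, 140 / 0.70 = 200. Both figures reproduce. No rate, effect, correlation or power is given for HADS.

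**Assumptions.** Control case rate 35% at every visit; palliative care rate 35% at baseline and 20% at week 12; equal correlation ρ between visits; complete data. The effect is either constant from week 6, or half-size at week 6 and full at weeks 12 and 24.

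**Dilution if baseline is pooled under one arm term.**
- Constant effect: (0 + 15 + 15 + 15) / 4 = 11.25 points, 75% of 15.
- Half effect at week 6: (0 + 7.5 + 15 + 15) / 4 = 9.4 points, about 63% of 15.
- Constant effect with assumed completion of 100/85/75/60%: 15 × (0.85 + 0.75 + 0.60) / 3.20 = 10.3 points.

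**Power formula.** For a mean over K visits, each arm's variance per person is V = [Σ p(1−p) + 2ρ Σ √(p(1−p)p′(1−p′))] / K², with the second sum over pairs of visits. SE = √((V_control + V_PC) / 140). Power = Φ(Δ/SE − 1.96).

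Worked case, constant effect, ρ = 0.5:
- Four visits: V = 0.1422 and 0.1100; SE = 0.0424; 0.1125 / 0.0424 = 2.65; power 0.76.
- Weeks 6, 12 and 24: V = 0.1517 and 0.1067; SE = 0.0430; 0.150 / 0.0430 = 3.49; power 0.94.
- Week 12 alone: SE = √((0.2275 + 0.16) / 140) = 0.0526; 0.150 / 0.0526 = 2.85; power 0.81.

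Adding the baseline row barely changes the standard error and cuts the estimate by a quarter.

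| Effect | ρ (0/1 scale) | Four visits, one arm term | Average of weeks 6–24 | Week 12 alone |
|---|---|---|---|---|
| Constant | 0.2 | 0.91 | 0.99 | 0.81 |
| Constant | 0.3 | 0.86 | 0.97 | 0.81 |
| Constant | 0.42 | 0.80 | 0.95 | 0.81 |
| Constant | 0.5 | 0.76 | 0.94 | 0.81 |
| Constant | 0.6 | 0.71 | 0.91 | 0.81 |
| Half at week 6 | 0.2 | 0.78 | 0.93 | 0.81 |
| Half at week 6 | 0.3 | 0.71 | 0.89 | 0.81 |
| Half at week 6 | 0.42 | 0.63 | 0.85 | 0.81 |
| Half at week 6 | 0.5 | 0.59 | 0.82 | 0.81 |
| Half at week 6 | 0.6 | 0.54 | 0.78 | 0.81 |

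With 30% vs 20% and a constant effect, power over the same range of ρ is 0.62–0.40 for four visits, 0.81–0.62 for the post-baseline average, and 0.49 for week 12.

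**Value of baseline adjustment.** I simulated 35% vs 20%, 140 per arm, with correlated normal variables cut at the case threshold. Latent correlations of 0.5, 0.7 and 0.8 correspond to roughly 0.31, 0.47 and 0.57 on the 0/1 scale. Without adjustment, week-12 power is about 0.82 (0.79 to 0.82 across runs; 0.81 by formula). With a continuous baseline score as covariate it is 0.86–0.95, rising with the correlation. With baseline case status only, it is about 0.84–0.93.

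**The case against.** A reader might infer that the plan's HADS test includes baseline as a response, and so is diluted as written. The documents do not say so. Section 11.4.2.1 is silent on baseline; the four-time-point wording belongs to FACT. Baseline as covariate, or an arm-by-visit model with a week-12 contrast, fits the sentence equally well, and an arm-by-visit model has no dilution. The dilution is therefore conditional.

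A reader might also infer that a test across visits is the wrong test. It is not: the endpoint includes the over-time part, and a smaller week-6 effect is legitimately part of it. What is missing is the 12-week contrast.

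Nor is a power loss general. With a constant effect and ρ of 0.2–0.3, the pooled four-visit test beats a plain week-12 test (0.91–0.86 vs 0.81). It falls behind when ρ exceeds about 0.42, or when the effect builds up.

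Finally, the plan calls other secondary findings exploratory, and it does not name HADS as the gate within the caregiver step. That limits the consequence. It does not supply the missing definition, nor does it explain leaving baseline HADS unused.

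**Conclusion.** The point holds as a gap in specification with a cheap improvement available. On any reading, the 12-week HADS endpoint has no named contrast and baseline HADS has no stated use.

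If baseline were pooled under one arm term, the estimate would be 75% of a constant effect (about 63% with half effect at week 6). Power would be below the post-baseline average in every scenario computed. Against an unadjusted week-12 test, the loss depends on correlation and time course.

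All rates, correlations and effect patterns are assumptions. The power figures are for patients only. The plan expects about 300 caregivers, roughly 150 per arm before missing data, and no caregiver power was computed. The test's size is correct when there is no effect at any visit, and the primary FACT-G conclusion is untouched.

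**What to change.** In 11.4.2.1, and so in 11.4.2.2, replace the association sentence with wording such as:

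*HADS case status at weeks 6, 12 and 24 is the response in a repeated-measures generalized linear model with arm, visit, arm-by-visit and the baseline HADS subscale score as covariate. The week-12 risk difference and relative risk, standardised over the baseline covariate, give the result at 12 weeks. The average arm contrast over weeks 6, 12 and 24 gives the result over time. Baseline is not part of the response.*

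Keeping baseline in the response with the arms constrained equal there, plus arm-by-visit terms and the same two contrasts, would also be acceptable. The essential step is to name one model before the data are seen.

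The cost is SAP wording; every measurement is already scheduled. The one small addition is a rule for participants with no baseline HADS, such as mean imputation of the covariate or a missing indicator.

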6.4 Chart Abstraction

The following data regarding measures of health service utilization and EOL care will be submitted using Medidata Rave® through chart abstraction by site staff at 1, 2, and 3 years (from enrollment) and at death.

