7.4 Duration of Follow-Up

Survival follow-up will be every 4 months from week 24 until death or up to 3 years (with chart abstraction at death, per section 6.4). Chart abstraction will be performed at year 1, 2, and 3 from enrollment, per section 6.4.

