10.0 END OF INTERVENTION

10.1 Duration of Intervention

The patient case evaluations will continue until the patient is deceased.

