11.2.2 Accrual Rate and Accrual Duration

We anticipate being able to accrue approximately 20 patients per month based on our best estimate for this new area of research. Using this estimate, we would complete accrual within 20 months and data maturation within 26 months from study initiation.

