11.3.2 Analysis Plan

A modified intent-to-treat principle³⁸ will be applied for statistical analysis of efficacy in evaluable patients. Evaluable patients are defined as all patients meeting the eligibility criteria who did not cancel prior to receiving intervention.

The primary analysis is to compare the change in FACT score from baseline to 12 weeks between study arms. We will perform preliminary analyses to examine how much QOL data are likely missing at random (MAR) or missing not at random (MNAR). However, missing data are expected to be MNAR as patients with poor QOL tend to have lower chances of completing a questionnaire, especially immediately prior to death.⁶⁶ We will examine the

pattern of missing data by comparing average scores among patient subsets defined by their available data and survival status. We will then use the pattern mixture models^{67,68} to adjust for MNAR bias by stratification based on survival data. We will compare study arms overall by weighting the within-stratum estimates with the estimated probability of being in each distinct combination of intervention arm and survival duration.

Sensitivity analysis will be conducted by exploring imputation method such as the last-observation carried forward, and the worst rank score analysis⁶⁹, favoring the more conservative method.

In the pattern mixture model, repeated measures of FACT will all be included in the repeated measures model to estimate the change from baseline to 12 weeks for primary analysis. Selected demographic and clinical factors (including stratification factors) may be incorporated when examining change in QOL scores across the four time points (baseline, 6, 12, and 24 weeks).

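### Does the Mann-Whitney comparison of hospital, ICU and hospice days need its own stated window and population?

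*Combined protocol and SAP*

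**What the plan says.** Section 11.4.1.3 lists two endpoints of this kind: "Rate of referral, enrollment and length of stay on hospice" and "Number of hospital and ICU admissions and days". Section 11.4.2.3 gives the method in one clause: "we will also compare days on hospice and in the hospital and ICU using the Mann-Whitney U test". Its next sentence plans Kaplan-Meier estimates and a log-rank test for survival.

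The timing is set elsewhere. Section 6.4 obtains health-service use through "chart abstraction by site staff at 1, 2, and 3 years (from enrollment) and at death". Section 7.4 adds: "Survival follow-up will be every 4 months from week 24 until death or up to 3 years". Section 10.1 says "The patient case evaluations will continue until the patient is deceased", under a heading about the duration of the intervention. Section 11.2.2 projects that "we would complete accrual within 20 months and data maturation within 26 months from study initiation".

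The population is defined in section 11.3.2, which applies modified intention-to-treat to efficacy analyses: "Evaluable patients are defined as all patients meeting the eligibility criteria who did not cancel prior to receiving intervention". Section 11.1 describes the trial's efficacy question as covering end-of-life care and resource utilization as well as reported outcomes.

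**The concern.** Three things are unwritten for this test: the calendar cut-off, whether non-enrollees count as zero hospice days, and how patients still alive are handled. Each could alter the result.

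- **Time alive.** A patient who lives longer has more time in which to be admitted. Section 1.1 reports survival more than two months longer with early palliative care in the earlier single-institution trial, so unequal survival is a realistic scenario.
- **Cut-off.** Month 26 and three years after the last enrollment give different data sets.
- **Hospice population.** Length of stay suggests enrollees only, whereas days on hospice suggests a count with zeros. If early palliative care adds users with short stays, the two readings can point in opposite directions.

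Fewer hospital and ICU days and more hospice use are Aim 2 hypotheses (section 1.3). The family is tested at 5% if the earlier gates pass, so a choice made with the data in hand would matter.

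**Working it through.** The plan gives no design figure for these endpoints, so there is none to reproduce. Survival, admission and hospice parameters below are assumptions, except that the 2-month gap echoes section 1.1 and medians under one year follow section 1.2.

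**1. Window.** The only source described for these days is the section 6.4 abstraction, bounded by section 7.4 at death or 3 years. Sections 10.1 and 7.3 concern the duration of the intervention and set no analysis window. Month 26 is 6 months after accrual ends (26 − 20). The week-24 questionnaire plus its 2-week window is 26 weeks, or 182 days, about 6 months. Month 26 therefore fits the questionnaires (an inference); three-year abstraction for the last patient ends near month 20 + 36 = 56.

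**2. Patients alive at 3 years.** With exponential survival, the proportion alive at 36 months is 2^(−36/median). Median 9: 2^(−4) = 6.25%, or 12.5 of 200. Median 11: 2^(−3.27) = 10.3%, or about 21 of 200. Few patients depend on the rule for the living.

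**3. Hospital days, identical use, 200 per arm, totals to death or 36 months.** Gamma-Poisson days, mean about 12 in the 9-month arm, 5,000 replicates. Entries are the percentage of trials significant for more / fewer days with early palliative care (nominal 2.5% each):

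| Medians (standard v early), months | 0% of use in last 30 days | 50% | 75% | 100% |
|---|---|---|---|---|
| 9 v 10 | 5.8 / 0.9 | 3.1 / 1.6 | 2.7 / 2.2 | 1.2 / 4.2 |
| 9 v 11 | 12.6 / 0.3 | 5.7 / 1.2 | 2.9 / 2.1 | 0.6 / 7.8 |

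At 9 v 9 every entry lies between 2.4 and 2.9. The direction depends on when use occurs, which the documents do not quantify. Section 1.2 does describe rising admission rates in the final month of life, so the 0% column is an extreme.

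**4. Would stating the window help?** With follow-up to death or 3 years and a cut-off at month 56, the 9 v 11 rates for more days are 11.3 / 5.6 / 2.4 / 0.8%. That is essentially the same pattern.

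**5. Would a rate per month alive help?** It depends on timing again. Mean time alive to 36 months is (median/ln 2) × (1 − 2^(−36/median)): 12.98 × 0.9375 = 12.2 months and 15.87 × 0.897 = 14.2 months.

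- If use is even over life, at 0.3 admissions a month and 5 days each, totals are 0.3 × 5 × 12.17 = 18.3 and 0.3 × 5 × 14.23 = 21.3 days. The rates are then equal.
- If all use is in the last month and identical per death, the rate is proportional to deaths per month alive. The ratio is (0.897/14.23)/(0.9375/12.17) = 0.82, an apparent 18% reduction with no difference in terminal care.

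Neither summary is neutral under both patterns.

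**6. Hospice, worked example, 180 deaths per arm.** Standard care: 100 users at 20 days, 80 zeros. Early palliative care: 100 at 20, 35 at 5, 45 zeros. P is the probability that an early-care patient has more days, ties counted half.

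- With zeros: (100/180)(0.5 × 100/180 + 80/180) + (35/180)(80/180) + (45/180)(0.5 × 80/180) = 0.401 + 0.086 + 0.056 = 0.543.
- Enrollees only: (100/135)(0.5) = 0.370.
- If the 35 added stays are also 20 days: with zeros, (135/180)(0.722) + 0.056 = 0.597; enrollees only, 0.500.

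Reversal therefore needs shorter added stays. In simulation (60% enrollment, mean stay 25 days, 10 points added), equal-length added stays give a significant gain in 41.5% of trials with zeros and 2.3% among enrollees. Added stays averaging 8 or 4 days give a gain in 22.8% or 15.0% with zeros, and an apparent loss in 16.0% or 27.9% among enrollees. Both results are significant in the same trial in only 0.4% or 1.0%.

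**7. All patients or decedents?** With enrollment 50% v 70%, median stay 20 v 14 days and 90% dead, P is 0.566 in all randomized and 0.571 in decedents, significant in 68% and 67% of runs. That choice hardly matters.

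**The case for a change.** The strongest case is that the text really is silent and that power can suffer. If use is even over life and early palliative care cuts the monthly rate by 20%, the chance of showing fewer days on 3-year totals falls from 21% with equal survival to 4% at 9 v 11 months. A per-time analysis keeps 34%. A month-26 cut-off would also leave 32% to 39% of patients in follow-up (medians 9 and 11, accrual uniform over 20 months).

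The silence stands. The rest is weaker. In that 4% scenario mean totals are 18.3 v 17.1 days, so the test correctly reports that total use barely differs. Section 1.3 hypothesises fewer days, not fewer per month alive; preferring a rate is a choice of estimand, with the drawback in step 5.

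For hospice, an enrollee-only test conditions on something that happens after randomization, and so does a decedent-only test. Neither is a clear improvement on counting all evaluable patients. Section 1.1 reports improved length of hospice stay in the earlier trial, which does not suggest that added stays would be short.

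**Conclusion.** No change is needed. The missing details have a natural reading: enrollment to death or 3 years, in all evaluable patients, with zero hospice days for those who never enroll. Stay among enrollees can be described alongside the enrollment rate, as the endpoint list already implies. Hospital and ICU totals should be read beside the survival comparison that section 11.4.2.3 already contains.

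The possible distortion is nil with equal survival. At 9 v 11 months it is about 3% to 6% against 2.5% in the direction of more days when half to three-quarters of use is terminal, and 8% to 13% only at the extremes. These figures rest on exponential survival and assumed patterns of use. The hospice reversal rests on an assumed and unsupported gap between added stays of 4 to 8 days and existing stays of 25. The analysis is secondary and is tested formally only if two earlier gates pass. Writing the window down would not alter the behaviour of the test, and changing the summary or population would exchange one limitation for another.
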